7.2 PARTICIPANT DISCONTINUATION/WITHDRAWAL FROM THE STUDY

Participants may be withdrawn from the study at any time for voluntary reasons or discontinued from study treatment at the request of the study investigators. Reasons for withdrawal or termination may include but are not limited to: 1) Subject requests discontinuation of study drug or withdrawal; 2) Subject becomes pregnant; 3) Subject requires treatment that is not permitted per protocol due to a risk for a drug interaction.

7.3 LOST TO FOLLOW-UP

Participants who do not return to their clinic appointment for a required study visit will be contacted by telephone immediately to reschedule their appointment. They will be counseled on the importance of maintaining the assigned visit schedule and ascertain whether they wish to continue in the study.

Before a subject is deemed lost to follow-up, the investigator or designee will make every effort to regain contact with the subject (where possible, 3 telephone calls and, if necessary, a certified letter to the participant's last known mailing address or local equivalent methods). These contact attempts will be documented in the participant's medical record or study file.

Should the subject continue to be unreachable, he or she will be considered to have withdrawn from the study with a primary reason of lost to follow-up. Data collected on study participants to the point of withdrawal will remain a part of the study record.

8 ASSESSMENTS

8.1 EFFICACY ASSESSMENTS

Initial screening will be completed by telephone after a potential subject seeks interest in study participation. This initial screening will include review of the study protocol inclusion/exclusion criteria. If the subject meets eligibility criteria, they will be asked to come into the research clinic to start the informed consent process and undergo screening laboratory testing.

8.1.1 Screening Visit

All participants will be informed of the nature and purpose of the study, and their written informed consent will be obtained prior to any study related activities. The investigator or designated qualified individual will perform the physical examinations. A physical examination will include measurement of body weight and height, general assessment of the skin, nose/throat, heart, lungs, and abdomen. The subject's total body weight and supine vital signs (heart rate, blood pressure, temperature, and respiratory rate) will be recorded.

Clinical Laboratory Testing and Urine hCG

- Serum comprehensive metabolic panel will be done including blood levels of albumin, blood urea nitrogen, calcium, carbon dioxide, chloride, creatinine, glucose, potassium, sodium, total bilirubin and protein, and liver enzymes (alanine aminotransferase, alkaline phosphatase, and aspartate aminotransferase).
- Serum hemoglobin will be measured.
- Urine human chorionic gonadotropin (hCG) will be measured for females who are not diagnosed as postmenopausal.

8.1.2 Study Visits

Participants (in cohorts of 6) will present to the Michigan Clinical Research Unit on their scheduled dosing day, and will be asked to have not consumed any food for at least 2 hours and any alcohol for at least 12 hours prior to this visit. A urine pregnancy test will be performed to rule out pregnancy prior to administration of the intranasal insulin dose to applicable female participants. The subject's total body weight and supine vital signs (heart rate, blood pressure, temperature, and respiratory rate) will be recorded. Eligible Participants will proceed with the study procedures after review of inclusion and exclusion criteria.

Participants will be asked to participate in 6 administrations over 5 sessions with a 1-week washout interval between each session. The first session will include an initial control administration of 0 U with 4 hours of observation, then followed by the first dose-escalation intranasal insulin administration and another 4 hours of observation. Subsequent visits will involve a single dose-escalation administration per visit as described in 6.1.2 Dosing and Administration. Any subject experiencing severe hypoglycemic episode will be given 100 U less than the last administered dose for the remainder of the study. Any participant having a second event, will be withdrawn from the study.

Participants will have peripheral intravenous access established with the placement of a short-term IV catheter for serial blood sampling and administration of supplemental glucose if needed. 5 mL of venous blood samples (3 mL as waste and 2 mL for blood glucose, insulin, and C-Peptide analyses) will be collected at 0, 15, 30, 60, 120, 180, and 240 minutes after each intranasal drug administration. Blood glucose levels will be measured with a point of care glucometer. The remaining blood samples will be centrifuged, aliquoted, and frozen for serum insulin and C-Peptide analyses by the University's Pharmacokinetics Core.

If a subject's blood glucose level falls <45 mg/dL, he/she will be treated with 50 ml of intravenous D50W and provided food. He/she will be monitored until achieving two consecutive measurements of blood glucose > 70mg/dL, measured at 30 minutes apart. If blood glucose falls to ≤70 mg/dL but not <45 mg/dL, the blood glucose will be monitored every 30 minutes until it returns to >70 mg/dL. Participants will not be released to home until any symptoms of hypoglycemia have resolved. Participant-reported adverse events will also be tracked as supplemental outcomes.

8.2 SAFETY AND OTHER ASSESSMENTS

- Vital Signs (blood pressure, pulse, respiratory rate, temperature)
- Clinical laboratory tests including blood chemistry and hematology parameters
- Urinalysis pregnancy screening test(s) in women
- Adverse events
- Concomitant medication use
- Physical exam

8.3 ADVERSE EVENTS AND SERIOUS ADVERSE EVENTS

8.3.1 DEFINITION OF ADVERSE EVENTS (AE)

The internationally accepted definition of an adverse event (AE) is any untoward medical occurrence in a patient or clinical investigation subject administered a pharmaceutical product and that does not necessarily have a causal relationship with this treatment. An AE can therefore be any unfavorable and unintended sign (including an abnormal laboratory finding), symptom, or disease temporally associated with the use of a medicinal product.

8.3.2 DEFINITION OF SERIOUS ADVERSE EVENTS (SAE)

A serious adverse event (SAE) is any AE occurring at any dose that results in any of the following outcomes: a life-threatening situation, death, inpatient hospitalization or prolongation of existing hospitalization, persistent or significant disability or incapacity, congenital anomaly or birth defect, or important medical events such as those that may not result in death, be life-threatening, or require hospitalization may be considered an SAE when based upon appropriate medical judgment. It jeopardizes the subject or requires medical or surgical intervention to prevent one of the outcomes listed above.

8.3.3 CLASSIFICATION OF AN ADVERSE EVENT

8.3.3.1 SEVERITY OF EVENT

The severity of adverse events will be graded using the [Common Terminology Criteria for Adverse Events \(CTCAE\) – NIH/NCI](#)

Grade 1:	Mild AE
Grade 2:	Moderate AE
Grade 3:	Severe AE
Grade 4:	Life-Threatening or Disabling AE
Grade 5:	Death related to AE

8.3.3.2 RELATIONSHIP TO STUDY INTERVENTION

The study physician will use clinical judgment to define a necessary medical course. AEs of interest are those that occur after the first dose of study medication. The relationship of AEs to the investigational product should be determined by the Investigator using the definitions below:

- Definitely related: clearly associated with study drug/treatment
- Probably related: likely associated with study drug/treatment
- Possibly related: may be associated with the study drug or other treatment
- Unlikely to be related
- Unrelated to the study drug

8.3.3.3 EXPECTEDNESS

The investigators will be responsible for determining whether an AE is expected or unexpected. An AE will be considered unexpected if the nature, severity, or frequency of the event is not consistent with the risk information previously described for the study agent in the protocol, informed consent, or labeling for the Humulin R U-500

8.3.4 TIME PERIOD AND FREQUENCY FOR EVENT ASSESSMENT AND FOLLOW-UP

The intranasal insulin dose administration will be managed by the study personnel. The participant will be directly monitored by study staff for the initial 4 hours after dose administration. AE assessments will occur during each study visit.

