1.3 SCHEDULE OF ACTIVITIES (SOA)

Schedule of Events table						
Study Visits	Screening	1	2	3	4	5
Study Day(s)	-28	0	7+/-3	14+/-3	21+/-3	28+/-3
Provide study overview and participant responsibilities	X					
Informed consent	X					
Medical history and inclusion/exclusion criteria review	X					
Previous and concomitant medications	X	X	X	X	X	X
Physical examination	X					
Vital signs ¹	X	X	X	X	X	X
Urine pregnancy test (female subjects of child bearing potential)	X	X	X	X	X	X
Insertion of a short term intravenous catheter		X	X	X	X	X
Study drug administration ²		X	X	X	X	X
Clinical laboratory screening labs ³	X					
POC serum glucose ⁴		X	X	X	X	X
Serum C-Peptide ⁵		X	X	X	X	X
Serum Insulin ⁵		X	X	X	X	X
Adverse event reporting		X	X	X	X	X

¹ Vital signs include blood pressure, pulse rate, respiration rate, and temperature at supine position.

² Study drug will be administered intranasally.

³ Clinical laboratory screening labs include clinical comprehensive metabolic panel and CBC.

⁴ Point-of-care (POC) serum glucose glucometry will be performed at 0, 15, 30, 60, 120, 180, and 240 minutes after each intranasal insulin administration. Sample will be collected +/- 10 minutes of scheduled assessment.

⁵ Blood and plasma samples will be collected, aliquoted, and frozen at 0, 15, 30, 60, 120, 180, and 240 minutes after each intranasal insulin administration for blood insulin and C-Peptide measurements by the University of Michigan Pharmacokinetics Core. Sample will be collected +/- 10 minutes of scheduled assessment.

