4.4 END OF STUDY DEFINITION

A participant is considered to have completed the study after he/she has completed all study visits as shown in the Schedule of Activities, Section 1.3.

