If there were 0 events in Cohorts 1 and 2, then the doses for Cohort 3 will be 0, 600, 700, 800, 900, and 1000 U. 400 U will be dropped and 700 U will be entered.

Cohort 4: Participants #19 to 24

Same as Cohort 3.

Other situations (more than one DLT)

Please also refer below to rules for discontinuing a dose.

If a dose (or doses) is dropped during or after a cohort, the highest available unused doses will be used for the next patients within that cohort and the next cohort. For example, if 1000 U is dropped, the future doses will be 200, 400, 600, 800 and 900 U. Or, if 800 U and all higher doses are dropped, then 200, 400, 500, 600, and 700 U will be the next set.

As one example, if there is 1 DLT in a different dose in each of the 4 cohorts, the trial will simply allocate using the initial rules for all cohorts, with the exception of the within subject adjustment rule noted above.

For example, if there are no DLTs in Cohort 1, then Cohort 2 will use 400, 600, 800, 900, and 1000 U. If Cohort 2 also has no DLTs, then 300 and 400 U will drop and Cohort 3 will use 600, 700, 800, 900, and

1000 U. Even if there are no DLTs in Cohort 3 given that allocation, we will continue that allocation as it utilizes the 5 highest available doses.

If higher doses are dropped, they cannot be reconsidered in the study.

If lower doses are dropped, they can re-enter the study. This would occur if higher doses needed to be dropped by having DLTs over the threshold. The lower doses may need to re-enter in order for each subject to have 5 potential doses.

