6.4 STUDY INTERVENTION COMPLIANCE

The study related activities, including drug administration and observation, will be performed with support from the Michigan Clinical Research Unit with an extensive track record of data integrity and compliance with regulatory procedures. Given that participants will be seen weekly, study compliance

will be reviewed at each visit. A record of any study queries, discrepancies, or deviations from the protocol will be maintained and provided to the study site and PI to resolve and document as a part of the study record. There are no subject diaries or study related activities that occur outside of subject visits.

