8.3.5 ADVERSE EVENT REPORTING

Out of range clinical laboratory findings (e.g., clinical chemistry, hematology, urinalysis) or findings on other assessments (vital signs) *per se* are not reported as AEs. However, those abnormal findings that are deemed clinically significant by the investigator or are associated with signs and/or symptoms must be recorded as AEs (and recorded as an SAE if they meet the criteria of being serious; see Section 8.3.2). The investigator should exercise medical and scientific judgment in deciding whether an out of range clinical laboratory finding or finding on other assessment is clinically significant.

All AEs occurring within 24 hours of study drug dosing and all SAEs occurring up until the last day of study participation will be recorded on the online AE case report form (CRF) through the study database. The investigators or Study Coordinator or designee is responsible for entering any and all AEs and SAEs into the database as soon as he/she becomes aware of the event and updating the information (e.g., date of resolution, action taken) in a timely manner. All non-serious AEs must be recorded on the electronic AE CRF within 5 days from the time it was discovered by the site study personnel.

Reporting of AEs and SAEs will follow the IRB standard AE reporting timeline.

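### The 24-hour adverse event commitment has no scheduled contact behind it after the final dosing visit, and in the planned escalation that gap falls mainly on the top dose

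*Combined protocol and SAP*

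**What the plan says.** The recording commitment is in section 8.3.5: "All AEs occurring within 24 hours of study drug dosing and all SAEs occurring up until the last day of study participation will be recorded".

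The means of finding those events are in section 8.3.4. The participant is "directly monitored by study staff for the initial 4 hours after dose administration", and "AE assessments will occur during each study visit". In the Schedule of Activities (section 1.3) the row "Adverse event reporting" is marked for Visits 1 to 5, and no column follows Visit 5. Section 6.4 adds: "There are no subject diaries or study related activities that occur outside of subject visits".

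On the end of participation, the synopsis counts participant duration from screening to the last visit, and section 4.4 says "A participant is considered to have completed the study after he/she has completed all study visits".

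On dose order, sections 4.1 and 6.1 have each participant move up through five active doses, one per visit. In the section 6.1.2 example with no DLT, 1000 U is last in every cohort; for instance, "the doses for Cohort 3 will be 0, 600, 700, 800, 900, and 1000 U".

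Section 10.1.6 says that observed and volunteered reactions are documented, and section 8.3.5 requires staff to enter an event once they learn of it. Neither sets up a contact.

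**The concern.** The plan promises a 24-hour window after each dose but actively covers only the first 4 hours. For Visits 1 to 4 the remainder can be recovered by asking at the next visit. After the final administration no later visit exists. Because doses ascend, the final administration is normally the participant's highest planned dose, so completeness of AE ascertainment is tied to dose.

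At stake is the AE profile by dose. The trial is described as a study of safety and tolerability (sections 2.1 and 4.1). Section 8.3.10 lists events to be tracked that need not begin within 4 hours, such as headache, rhinitis, rash and upper respiratory infection. Section 4.3 says most existing safety data lie between 20 and 160 U, so outside evidence can least make good a gap at 1000 U. A reader comparing AE counts across doses could take poorer ascertainment at the top for better tolerability.

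**Working it through.** The documents give no figure for this point, so there is none to reproduce. I counted administrations by dose and visit, then asked which have a later AE assessment.

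**Inputs.** 24 participants in four cohorts of 6; the no-DLT dose sets in section 6.1.2; one active dose per visit, ascending, with the 0 U control also at Visit 1; AE assessment at Visits 1 to 5 only.

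| Cohort | Visit 1 | Visit 2 | Visit 3 | Visit 4 | Visit 5 |
|---|---|---|---|---|---|
| 1 | 200 | 400 | 600 | 800 | 1000 |
| 2 | 400 | 600 | 800 | 900 | 1000 |
| 3 | 600 | 700 | 800 | 900 | 1000 |
| 4 | 600 | 700 | 800 | 900 | 1000 |

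**Count.** Six participants per cell:

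| Dose (U) | Administrations | With a later AE assessment |
|---|---|---|
| 200 | 6 | 6 |
| 400 | 12 | 12 |
| 600 | 24 | 24 |
| 700 | 12 | 12 |
| 800 | 24 | 24 |
| 900 | 18 | 18 |
| 1000 | 24 | 0 |
| Total | 120 | 96 |

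Below 1000 U the figure is 96 of 96; at 1000 U it is 0 of 24. The other full dose sets given as examples in section 6.1.2 (200/400/600/800/900, 200/400/500/600/700 and 200/300/400/500/600) also put their highest dose fifth.

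**Time without scheduled ascertainment.** 24 − 4 = 20 hours per final administration, or 20/24 = 83% of the window. Over 24 participants that is 24 × 20 = 480 participant-hours. Direct observation is 4 hours at every dose; what differs is whether someone asks later.

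**When the question is asked at lower doses.** With the ±3-day windows, Visit 2 falls 7 − 3 = 4 to 7 + 3 = 10 days after Visit 1. Later pairs of visits are (14 − 3) − (7 + 3) = 1 to (14 + 3) − (7 − 3) = 13 days apart. Coverage there is by recall, which is itself imperfect.

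**Direction of the effect.** Let p be the true rate of AEs starting at 4 to 24 hours, r the chance that such an event is recorded when a later visit exists, and v the chance when only volunteering is possible. The recorded rates are p × r and p × v, so the top dose is understated by the factor v/r relative to a lower dose with the same p. A later visit adds a route of capture, so v should not exceed r. The documents give neither value.

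**Illustration with assumed values.** The chance of recording at least one late AE among 24 participants is 1 − (1 − p × s)^24, where s is the capture probability.

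| Assumed p | s = 1 | s = 0.5 |
|---|---|---|
| 0.05 | 71% | 46% |
| 0.10 | 92% | 71% |
| 0.20 | 99.5% | 92% |

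Under the present schedule, s at 1000 U is whatever spontaneous reporting delivers, down to 0% in every row if nobody volunteers. A scheduled contact would raise s.

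**The case against.** The strongest reply is that nothing decisive depends on these hours. The DLT is a glucose value at a check during the visit (section 3). Dose removal (section 7.1) and MTD selection (sections 9.1 and 9.4.1) use only that. The synopsis and section 4.1 mention other adverse events in the Bayesian model, but the operating rule in section 7.1 counts none. A late event after Visit 5 cannot change that participant's dosing either. Section 8.1.2 calls participant-reported AEs supplemental, and no formal comparison of AEs between doses is specified. All of this stands. A reader might infer that the MTD is biased; the documents do not support that.

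Further limits also stand:

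- **Not a bar on collection.** Volunteered events are documented, and monitoring runs past 4 hours if glucose or symptoms of hypoglycemia have not recovered (section 8.1.2). Section 6.4 is not literally exhaustive, since sections 5.5 and 7.3 plan reminders and calls about missed visits. The consent form and the visit figure are not in the text available to me, so I draw nothing from their absence. What is missing is scheduled, active questioning.
- **Serious events (SAEs).** One might infer that any SAE after leaving Visit 5 lies outside collection. That is wrong: section 8.3.2 defines an SAE as an AE, so one within 24 hours of dosing is inside the window, though without scheduled capture. Only SAEs beyond 24 hours after Visit 5 fall outside it.
- **Not always the highest dose.** After a DLT the participant's later doses are lower, and a dose may be removed mid-cohort, so the highest dose can precede Visit 5. If 1000 U is removed late, the selected dose could be one given mostly at Visit 4. The 0 of 24 count belongs to the no-DLT allocation.
- **Not 83% of events missed.** That would need uniform onset and no volunteered reports. Several listed events are local nasal effects that may well begin early.

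None of this supplies a contact after the last dose.

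**Conclusion.** The point holds as a gap between the AE commitment in section 8.3.5 and the means provided in sections 1.3, 6.4 and 8.3.4. Hours 4 to 24 after the final administration have no scheduled ascertainment. The same is true after a visit at which a participant is withdrawn, for example after a second severe hypoglycemia under section 6.1.2.

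The schedule contrast rests on the no-DLT allocation and on participation ending at the last visit. The resulting bias in AE rates cannot be sized from the documents; only its likely direction, low at the top dose, can be stated. It bears on AE rates by dose, and on the dose-safety curves in section 9.4.4 if those use AEs. The primary endpoint and MTD are untouched, so I would rate this as something that should be fixed because the remedy is cheap, not as a flaw in the main result.

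**What to change.** - Add one scripted telephone AE/SAE contact at least 24 hours after Visit 5, and after any visit at which a participant is withdrawn.
- Give it a column in the Schedule of Activities (section 1.3) and mention it in section 8.3.4.
- Define that contact as the last day of participation in sections 4.4 and 8.3.5, so that SAE collection runs to it.
- Correct the sentence in section 6.4 that rules out activity outside visits.

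In the no-DLT allocation, 24 of 24 administrations at 1000 U would then have a scheduled AE assessment covering their full 24-hour window, up from 0 of 24. The cost is a small amendment and about 24 short calls; the site already plans calls, texts or emails as reminders (section 5.5). Calling after every dosing visit (24 × 5 = 120 calls) would also make the method of questioning the same at every dose, but it is optional and not needed to close this gap.

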8.3.5 ADVERSE EVENT REPORTING

Out of range clinical laboratory findings (e.g., clinical chemistry, hematology, urinalysis) or findings on other assessments (vital signs) *per se* are not reported as AEs. However, those abnormal findings that are deemed clinically significant by the investigator or are associated with signs and/or symptoms must be recorded as AEs (and recorded as an SAE if they meet the criteria of being serious; see Section 8.3.2). The investigator should exercise medical and scientific judgment in deciding whether an out of range clinical laboratory finding or finding on other assessment is clinically significant.

All AEs occurring within 24 hours of study drug dosing and all SAEs occurring up until the last day of study participation will be recorded on the online AE case report form (CRF) through the study database. The investigators or Study Coordinator or designee is responsible for entering any and all AEs and SAEs into the database as soon as he/she becomes aware of the event and updating the information (e.g., date of resolution, action taken) in a timely manner. All non-serious AEs must be recorded on the electronic AE CRF within 5 days from the time it was discovered by the site study personnel.

Reporting of AEs and SAEs will follow the IRB standard AE reporting timeline.

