8.3.10 DEFINITIONS OF SELECTED OR ANTICIPATED ADVERSE EVENTS

The adverse events identified below are anticipated and will be tracked.

Allergic reaction
 Aspiration
 Nasal irritation
 Sneezing
 Warm feeling in nostrils
 Congestion/Rhinitis
 Lightheadedness
 Nausea and vomiting
 Nosebleeds
 Hypoglycemia
 Headache
 Weakness
 Upper respiratory infection
 Rash

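### No contact is scheduled after the Visit 5 dose, so hours 4 to 24 of its AE window rest on spontaneous reports, and Visit 5 normally carries the top dose

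*Combined protocol and SAP*

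**What the plan says.** Section 8.3.5 sets two recording windows. For AEs it covers "All AEs occurring within 24 hours of study drug dosing", with no exception for any visit. For SAEs, "all SAEs occurring up until the last day of study participation will be recorded".

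Section 8.3.4 describes how events are found: the participant is "directly monitored by study staff for the initial 4 hours after dose administration", and "AE assessments will occur during each study visit". Section 6.4 adds: "There are no subject diaries or study related activities that occur outside of subject visits".

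The schedule in section 1.3 ends with Visit 5 at Day 28 ± 3. Section 4.4 states: "A participant is considered to have completed the study after he/she has completed all study visits". The synopsis (1.1) counts participant duration, up to 60 days, from screening to the last visit.

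Section 6.1.2 gives each participant five active doses in rising order, one per visit. Every allocation listed for the case without DLTs ends at 1000 U.

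**The concern.** The recording duty runs for 24 hours, but planned collection stops at about 4 hours unless a later visit follows. Visits 1 to 4 are each followed by another visit with an AE assessment. Visit 5 is not.

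For SAEs the written window itself differs by visit. An SAE starting three days after the Visit 4 dose falls inside it. One starting three days after the Visit 5 dose falls outside it, if participation ends on the day of Visit 5.

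Because dose order is visit order, the shorter follow-up coincides with the highest dose. What is at stake is any summary of AEs and SAEs by dose: low counts at 1000 U could reflect tolerability or shorter ascertainment, and the data could not separate the two. Section 4.1 says dose will be related to other adverse events as well as to hypoglycemia. Sections 2.1 and 4.3 want the result to inform a safety margin for community use.

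**Working it through.** **1. The plan's own duration figure.** Inputs from section 1.3: screening at Day −28 and Visit 5 at the latest on Day 28 + 3 = 31. Elapsed time is 31 − (−28) = 59 days, or 60 days counted inclusively. This reproduces the synopsis figure of up to 60 days and leaves no day for contact after Visit 5.

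**2. Share of the AE window with planned ascertainment after Visit 5.** Inputs: 24 hours (8.3.5) and 4 hours (8.3.4).
- Covered: 4/24 = 17%.
- Not covered: 24 − 4 = 20 hours; 20/24 = 83%.

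This is a share of hours, not of events.

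**3. Which dose carries the gap.** Inputs: the no-DLT allocations in 6.1.2, six participants per cohort.

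| Cohort | Visit 1 | Visit 2 | Visit 3 | Visit 4 | Visit 5 |
|---|---|---|---|---|---|
| 1 | 200 | 400 | 600 | 800 | 1000 |
| 2 | 400 | 600 | 800 | 900 | 1000 |
| 3 | 600 | 700 | 800 | 900 | 1000 |
| 4 | 600 | 700 | 800 | 900 | 1000 |

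1000 U is given 4 × 6 = 24 times, always at Visit 5, and no other dose is given there. On this path dose and shortened follow-up are completely confounded. The exception is a participant with severe hypoglycemia, who under 6.1.2 is moved to a lower dose and so does not receive the highest dose at Visit 5.

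**4. Illustration of size.** The two inputs here are assumptions; neither is in the documents. Let *f* be the share of 24-hour AEs that start after hour 4, and *r* the share of those reported spontaneously. The share detected at Visit 5 is 1 − *f*(1 − *r*).

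| *f* | *r* = 0 | *r* = 0.5 | *r* = 1 |
|---|---|---|---|
| 0.10 | 0.90 | 0.95 | 1.00 |
| 0.25 | 0.75 | 0.875 | 1.00 |
| 0.50 | 0.50 | 0.75 | 1.00 |

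If 6 of 24 participants truly had an AE at 1000 U and *f* = 0.25, the expected number recorded would be 6 × 0.75 = 4.5 with *r* = 0, and 6 with *r* = 1.

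**5. What does not change.** Section 3 defines the primary endpoint by glucose checks during the visit, and the last is at 240 minutes. The dose-removal rule (7.1) and the MTD definition (9.1, 9.4.1) use only that endpoint.

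**The case against.** Much of the case on the other side stands, and it limits the point.

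- **Spontaneous reports count.** Section 8.3.5 makes no exception for Visit 5 and requires entry once staff learn of an event. An SAE within 24 hours is also an AE within 24 hours, so the AE clause covers it. Section 8.3.6 states no participation cut-off for SAE reporting to the IRB and FDA. The consent pages, which might tell participants how to report later events, are not available for review. What is missing is a scheduled contact, not every route. Even so, passive capture at one dose against a scheduled assessment for the others is unequal.
- **Collection after Visits 1 to 4 is not spelled out.** Section 8.3.4 places an AE assessment at each visit but does not say that it asks about hours 4 to 24 after the previous dose. Complete recall at those visits cannot be assumed. If nobody asks, the gap exists at every dose.
- **The control is no better covered.** Section 6.1 gives the first active dose 4 hours after 0 U. The imbalance is mainly between 1000 U and the doses at Visits 1 to 4, much less between 1000 U and 0 U.
- **The end of participation is inferred.** The last day of participation is not defined. Equating it with Visit 5 rests on 4.4 and the synopsis, and is the natural reading.

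A reader might also infer that the dose-safety curves in 9.4.4 are biased throughout. The primary and secondary endpoints in section 3, which that section most plainly refers to, are all measured within 4 hours, and 8.1.2 treats participant-reported AEs as supplemental. Another tempting reading concerns upper respiratory infection, which is on the list introduced by "The adverse events identified below are anticipated and will be tracked" in 8.3.10. A non-serious infection starting after 24 hours lies outside the AE window at every dose, so its loss is not specific to the top dose.

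**Conclusion.** The point holds as a gap in AE and SAE ascertainment. After the Visit 5 dose, 20 of the 24 hours that 8.3.5 promises to cover have no planned collection, and the SAE window closes that day. On the no-DLT path this applies to all 24 administrations of 1000 U, so AE and SAE tabulations by dose are prone to under-counting there relative to doses given at Visits 1 to 4.

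The direction assumes that the AE assessment at Visits 2 to 5 picks up at least some events from the preceding interval, and that participation ends at Visit 5. The size cannot be derived, because the documents do not say how many AEs start after hour 4 or how many would be volunteered.

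A reader might infer that the MTD itself is at risk. It is not: the DLT endpoint, the dose-removal rule and the MTD use only glucose measured during the visit. This is a worthwhile, inexpensive improvement to safety collection and does not undermine the primary result.

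**What to change.** 1. Add one scheduled telephone AE/SAE contact at least 24 hours after the Visit 5 dose, and define it as the last day of study participation.
2. State that the AE assessment at each of Visits 2 to 5 asks about AEs in the 24 hours after the previous dose.
3. Reconcile the synopsis duration (1.1), the schedule (1.3) and sections 4.4, 6.4, 8.3.4 and 8.3.5 with this contact.

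The 24-hour AE window can stay as it is. Placing the call at about 7 days, to match the between-visit interval for SAEs, is optional.

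The cost is at most 24 short calls, an amendment and a restated duration. A 24-hour call moves the latest end from Day 31 to Day 32, which is 28 + 32 = 60 days elapsed (61 inclusive). A 7-day call moves it to Day 38, which is 28 + 38 = 66 days elapsed. Section 5.5 already provides for telephone, text or email reminders, so contacting participants remotely is not new to the study. The sample size and the dose rules do not change.
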